7.2 Administration of GuessWhat

We will include several screening steps prior to enrollment. These will include: (1) completion of a short screening questionnaire, (2) Completion of baseline measures online, Demographics age matches baseline DOB, Time to complete baseline >20 minutes (not required, but will be flagged if not met), Missing data <40% (not required, but will be flagged if not met), Commitment task where a parent is asked to upload a picture of their child participating and confirm they understand participant responsibilities.

A coordinator will complete the above screening steps, and if the participant meets all requirements, will randomize the participant. Treamtent participants will receive a link to download the app.

GuessWhat is administered by the parent initiating play with the child. The parent interacts with the child throughout gameplay to administer the treatment for the recommended dose.

The current trial's control is a treatment as usual group. Control participants will be asked to continue their treatment, and to inform the study team of any changes in treatment regimen during follow up assessments.

Treatment Compliance

After randomization and enrollment, research coordinators will monitor activity and contact participants by phone or email if there is no activity within the first 7 days. Participants will receive 3 reminders before being marked as lost to follow-up. The app will also send automatic notifications and automated email reminders will be sent weekly to remind parents to engage with the app.

Treatment Precautions

We identified no critical tasks during our use related risk analysis. We used simulated use to identify user tasks and determine associated hazards. To date No Adverse Events have been reported through testing. Following completion of Clinical Trial, we will include all adverse event information. We determined that use of the app presents no greater risk than a child and parent encounters in daily life.

Concomitant Therapy

We will not prohibit any concomitant therapy, pharmaceutical or behavioral. We will collect information on concomitant therapy and treatment at week 4, 8, 12.

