8.1 Screening and Enrollment Steps

Week 0/Screening and Baseline Assessment

Participants will be screened, consented, and enrolled entirely online using electronic data capture. Parents/Guardians and coordinators will complete the following steps prior to enrollment via online forms:

- Screening questionnaire completed online
- Informed Consent administered and obtained online (waiver of documentation approved)
- Baseline questionnaires completed (Demographics, Mobile Autism Risk Assessment (MARA), Parent Stress Scale, VABS-3 Socialization subscale parent report, Emotion Recognition Child online Task
- review of baseline data completed by coordinator

Week 1: Enrollment and Allocation

- Upon receiving notification with download link and download access code, participant downloads the app and is automatically randomized to treatment or control using a pre-defined block randomization scheme developed by the statistician.

[Weeks 1-4: Intervention](#)

If randomized to Control, participants will continue treatment as usual. When they log-in to the app, they will receive a message that they will wait a few more weeks before beginning treatment.

If randomized to Treatment, participants will be asked to play the app 3 times a week for 10-15 minutes for the next 4 weeks and they will receive weekly push notifications and email reminders.

[Week 4 Post-Test 1](#)

Treatment and Control will be asked to complete all outcome measures and will be asked about any changes in treatment or safety events at week 4. Participants will also be asked to complete a question assessing time spent playing with their child over the last month in emotion-centric theatrical play.

[Week 8 Post-test 2](#)

At week 4 from initial app download date, participants will be asked via email to complete all outcome measures as well as check-in on any changes in treatment and any safety events. These will be collected via RedCap online surveys.

[Week 12 Post-test 3 Follow-Up](#)

Treatment and Control will be asked to complete all outcome measures and will be asked about any changes in treatment or safety events at week 4. Participants will also be asked to complete a question assessing time spent playing with their child over the last month in emotion-centric theatrical play.

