10.4 Analysis Populations

The following analysis populations will be defined for the study:

- (1) The intent-to-treat (ITT) population will include all randomized patients. Patients will be analyzed according to their assigned treatment arm. All efficacy analyses will be completed in the ITT population.
- (2) Per-Protocol (Treatment Compliant): This population is defined as any participant that began the initial 4-week treatment or control phase, completed both the pre and post assessments, and met a minimum compliance level of 50%. Participants that received incorrect intervention after randomization will be excluded from this population.
- (3) The safety population will include all patients who receive study treatment. Patients will be analyzed according to actual treatment received. All safety analyses will be completed in the safety population.

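### Sections 7.2 and 8.1 state incompatible randomization procedures, so the ITT set is not fixed and concealment is unspecified under 7.2

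*Combined protocol and SAP*

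**What the plan says.** Section 7.2 (Administration of GuessWhat) lists the screening steps and continues: "A coordinator will complete the above screening steps, and if the participant meets all requirements, will randomize the participant". The next sentence reads: "Treamtent participants will receive a link to download the app". The arm is therefore known before that link goes out.

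Section 8.1, under Week 1, says: "Upon receiving notification with download link and download access code, participant downloads the app and is automatically randomized to treatment or control", and it does so "using a pre-defined block randomization scheme developed by the statistician". Under Weeks 1-4 it says of controls: "When they log-in to the app, they will receive a message that they will wait a few more weeks before beginning treatment". Here the link and the download come before the arm exists, and controls have the app.

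Section 10.4 says "The intent-to-treat (ITT) population will include all randomized patients" and "All efficacy analyses will be completed in the ITT population". Section 7.2 (Treatment Compliance) has coordinators contact participants who show no activity in the first 7 days and mark them as lost to follow-up after 3 reminders.

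**The concern.** The ITT definition depends entirely on the moment of randomization, and the document gives two such moments. A family cleared by the coordinator that never installs the app belongs to the ITT under 7.2 and does not exist for the analysis under 8.1. The primary analysis set, the CONSORT counts and the description of missing data all change with the choice.

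Two further matters follow. If allocation comes first, installing the app becomes a hurdle after randomization, and 7.2 states it for treatment participants alone. Joined to the inactivity rule, non-download could be recorded as loss in one arm. If allocation follows download, that hurdle is passed before the arms exist and cannot differ between them.

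The second matter is concealment. Section 4.2 gives recruitment and enrollment to a single coordinator. Under 7.2 the coordinator who clears eligibility also randomizes, and no safeguard is described. Outcome assessors are unblinded (4.1) and the primary outcome is a parent report (9.1), so concealed allocation is one of the few protections left.

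**Working it through.** **1. The two procedures side by side**

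| | Section 7.2 | Section 8.1 |
|---|---|---|
| Who assigns | Coordinator | Automatic |
| When | After screening, before treatment participants get the link | After link, access code and download |
| Source of the list | Not stated | Statistician's pre-defined block scheme |
| App for controls, weeks 1-4 | Not stated; a link is mentioned for treatment participants | Yes, with a waiting message |

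The order alone makes them incompatible: the arm must exist before the link in 7.2 and cannot exist until after it in 8.1. This holds even if controls were also sent a link under 7.2.

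**2. Whether another section settles it**

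Section 10.5 gives a 1:1 ratio and blocks of 2 or 4 after consent and eligibility, but names neither a person nor a system. The Section 13 schedule puts allocation at week 1 and App Download at weeks 0 and 4. (The table may have been disturbed in conversion.) As it reads, download and allocation fall in different columns, whereas 8.1 makes them one week-1 event. Neither section decides the matter. Section 8.1, under its Week 8 heading, also times a follow-up from the download date; 7.2 states no such date for controls.

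**3. Effect on the ITT set**

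Inputs from Section 10.2: up to 2,000 participants, 50% enrollment, 36% retention, 360 completers. The plan's figure reproduces: 2,000 × 0.50 × 0.36 = 360.

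Assumptions: the 2,000 × 0.50 = 1,000 families are those cleared by the coordinator, 360 of them complete, and the download rate p, which is not given, lies between 50% and 100%.

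- ITT under 7.2 = 1,000
- ITT under 8.1 = 1,000 × p
- Completers as a share of ITT = 360 / ITT
- Treatment families in the 7.2 ITT who never had the app = 500 × (1 − p)

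| p | ITT, 7.2 | ITT, 8.1 | Completers, 7.2 | Completers, 8.1 | Treatment families without app, 7.2 |
|---|---|---|---|---|---|
| 50% | 1,000 | 500 | 36% | 72% | 250 |
| 60% | 1,000 | 600 | 36% | 60% | 200 |
| 70% | 1,000 | 700 | 36% | 51% | 150 |
| 80% | 1,000 | 800 | 36% | 45% | 100 |
| 90% | 1,000 | 900 | 36% | 40% | 50 |
| 100% | 1,000 | 1,000 | 36% | 36% | 0 |

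**4. Predictability, as an illustration only**

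Assume that past allocations within a sex stratum are visible, that blocks of 2 and 4 are equally likely, and that the guesser always picks the under-represented arm.

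- Block of 2: expected correct guesses 0.5 + 1 = 1.5 (75%).
- Block of 4: 0.5 + 2/3 + 2/3 + 1 = 2.833 (70.8%).
- Equal mix: (1.5 + 2.833) / (2 + 4) = 72.2%, against 50% when concealed.
- Certain allocations: an imbalance of 2 arises only in a block of 4 whose first two assignments match (probability 1/3). It reveals the block size and fixes the last two. With a mean block length of 3, this is 0.5 × (1/3) × 2 / 3 = 11.1%.

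**The case against.** The strongest reply is that 7.2 is loose shorthand: the coordinator releases an eligible family to the app, and 8.1 describes the real mechanism. That may be so, but no section says it, and the statement in 7.2 about the link still presupposes a known arm.

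Three stronger readings are tempting and are not supported.

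- *Controls have no app under 7.2.* The text mentions a link for treatment participants. It does not say that they alone receive one. The inference is reasonable, but it is not what the protocol states.
- *The coordinator can steer allocation.* A coordinator can trigger a concealed list, and nothing says this one sees the list or past assignments. Coordinators also monitor app activity, so past allocations might become known under 8.1 too. The 72% and 11% therefore do not measure the cost of 7.2 relative to 8.1. The block-size mix is also assumed, and a guesser would have to track each sex stratum separately.
- *The 64% loss implied by 36% retention shows the scale of non-download.* Section 10.2 does not break that loss down. Under 8.1 enrollment and allocation coincide with download, so non-downloaders would never have been counted as enrolled.

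It is also fair to say that non-download is first of all non-adherence. Section 8.1 describes outcome collection by emailed online survey, so such a family could still give week 4 data. It becomes loss only if the inactivity rule is applied to stop follow-up, which is possible but not shown.

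**Conclusion.** The contradiction stands on the text alone, and so does its consequence for the ITT: two different sets of families would enter every efficacy analysis. The size is unknown because no download rate is given. Over the assumed 50% to 100% range, the sets differ by 500 families down to none out of 1,000.

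One-arm loss under 7.2 is a plausible consequence that depends on how the inactivity rule is applied. On concealment, the supportable statement is that 8.1 ties automatic assignment to the statistician's list, whereas 7.2 specifies no safeguard. The predictability figures only indicate why small blocks need a stated safeguard. The inconsistency should be resolved before the analysis, because the primary population cannot be identified from the document as written.

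**What to change.** Adopt the 8.1 process throughout:

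- The coordinator clears eligibility without access to the allocation list.
- Both arms receive the link and access code.
- The system allocates automatically at download, once baseline is complete.
- Section 7.2: amend the sentences on randomization and on the link to match.
- Section 13: align the App Download and Allocation rows with this order.
- Section 10.4: state that ITT is everyone so allocated, whether or not they go on to play.

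The cost is small if the automatic allocation described in 8.1 is operating. The document describes that function but does not show that it works; if it does not yet, this is a modest operational change. The trial would then estimate the effect among families who install the app, which should be said. The inactivity rule would still bear on treatment families who install and do not play, so the change removes only the download part of any one-arm loss. If enrollment has begun, the sponsor should report which procedure was actually used.

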10.2 Sample Size Justification and Power Calculation

We will enroll up to 2,000 participants to achieve a 50% enrollment rate and 36% retention rate.

We aim to successfully retain 36% of enrolled families and have 360 parents and their child with autism aged 3-12 years old complete all study procedures (180 Treatment, 180 Control).

We will close out the study after enrolling 360 participants with completed endpoints, estimated for 90% power and 2-sided significance of .05 to detect minimal differences in VABS-III Socialization Standard Score of 3.1 points, consistent with the results of a GuessWhat feasibility study previously reported by our lab.

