10.5 Stratification, Subgroup Analysis and Pooled Analysis

Following consent, those subjects meeting all entry criteria will be randomized in a 1:1 ratio. Random blocks of size 2 or 4 will be utilized.

[Efficacy Endpoint Analysis](#)

1. Objective

To compare the change in outcome measure scores between treatment and treatment as usual groups in a clinical trial.

2. Study Design

Participants: Treatment and Treatment as Usual groups

Outcome Measure: Continuous outcome measure scores measured at baseline and follow-up on VABS-3 Socialization Subscale and Parent Stress Scale.

3. Statistical Hypotheses

Null Hypothesis (H_0): There is no difference in the change in outcome measure scores between treatment and control groups.

Alternative Hypothesis (H_1): There is a significant difference in the change in outcome measure scores between treatment and control groups, whereby treatment participants scores demonstrate improvement.

4. Variables

Independent Variable: Group (Treatment vs. Control)

Dependent Variable: Change in outcome measure scores (Post-test score - Pre-test score)

5. Statistical Method

Primary Analysis: Independent samples t-tests will be used to compare the mean change in outcome measure scores between treatment and control groups.

6. Assumptions

Normality: The change in outcome measure scores in each group should be approximately normally distributed. If not, consider transformations or non-parametric tests.

Equal Variances: The variances of change scores in the treatment and control groups should be approximately equal. If violated (checked using Levene's test), use Welch's t-test or report results with caution.

7. Statistical Software

Analysis Tool: SPSS, R, or any other statistical software capable of performing independent samples t-tests.

Descriptive analyses

Descriptive statistics (proportions for categorical variables, means, medians, standard deviations, and interquartile ranges for continuous variables) will be reported for all key patient variables, including baseline and demographic characteristics, use of medications, compliance, and study completion status. Data that are missing on key patient characteristics and the outcome will be fully described, including any patterns of missingness (i.e., any relationships between missingness of a variable and patient characteristics).

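### Section 7.2 can be read as turning app inactivity into loss to follow-up, which could select the treatment arm of the primary t-test and leave controls unselected

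*Combined protocol and SAP*

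**What the plan says.** **The inactivity rule.** In section 7.2, under Treatment Compliance, coordinators watch activity after randomization and "contact participants by phone or email if there is no activity within the first 7 days". The next sentence is "Participants will receive 3 reminders before being marked as lost to follow-up". The one after it describes app notifications and weekly emails that prompt parents to use the app.

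**What controls can do.** Under section 8.1, controls who log in learn only that "they will receive a message that they will wait a few more weeks before beginning treatment". The weekly push and email reminders are listed there for the treatment arm only.

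**Week-4 collection.** Section 8.1 says of week 4: "Treatment and Control will be asked to complete all outcome measures". It makes no exception for inactive families, and it does not mention families already marked lost.

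**Analysis.** Section 10.4 defines ITT as everyone randomized and adds: "All efficacy analyses will be completed in the ITT population". Section 10.5 makes the primary analysis an independent-samples t-test on post-test minus pre-test change. On missing outcomes it says only: "Data that are missing on key patient characteristics and the outcome will be fully described".

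**Stopping.** Section 10.2: "We will close out the study after enrolling 360 participants with completed endpoints". The target is 180 per arm, with planned retention of 36%.

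**The concern.** Stopping treatment and stopping outcome collection are different events, and an ITT comparison depends on keeping them apart. Read in sequence, section 7.2 goes from no activity, through reminders, to lost to follow-up, and so merges them.

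If the mark means that the family is not asked for the week-4 Vineland, three other features of the plan turn that into selection:

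- A change score cannot be formed without a week-4 score, so the family drops out of the t-test whatever the ITT label says.
- No method for missing outcomes brings the family back in.
- Enrollment runs until 360 families have completed endpoints, so another family takes its place.

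The treated group would then be families who started to play, and the control group everyone who answers. Families who engage may report more improvement for reasons unrelated to the app, such as motivation, available time or expectation. A difference could then appear with no app effect. If the app does work, the result would be the effect in players under an ITT label. With 64% of families expected to be lost, a shift in who remains in one arm would be hard to notice.

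**Working it through.** **1. The plan's own figures.** Recruitment reproduces: 2,000 × 0.50 × 0.36 = 360. The power statement cannot be reproduced directly because no SD is given, so it is solved for the SD. For 180 per arm, 90% power and two-sided 0.05, the t-test needs a standardized difference of 0.3426. The implied SD is 3.1 / 0.3426 = 9.05, and the standard error of the difference is 9.05 × √(2/180) = 0.954. (The normal approximation gives an SD of 9.07.)

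**2. Assumed inputs, not in the documents.**

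- *s*: among treated families who would return week-4 measures, the share marked lost for inactivity and therefore not asked. Range 10% to 30%.
- *d*: points by which non-playing families change less than playing families for reasons other than the app. Range 0 to 5. The feasibility study in section 3.2 reports a gain of 5.27, but that is an uncontrolled pre-post change and only gives a sense of scale.

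**3. No app effect.** Let players change by m on average. Controls are unselected, so their mean is (1 − s)m + s(m − d) = m − s·d. The retained treated families have mean m. The spurious difference is s·d. Type I error comes from the noncentral t with 358 degrees of freedom and noncentrality s·d / 0.954.

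| s | d | Spurious difference (points) | Type I error |
|---|---|---|---|
| any | 0 | 0 | 5.0% |
| 10% | 1 | 0.1 | 5.1% |
| 10% | 3 | 0.3 | 6.1% |
| 20% | 3 | 0.6 | 9.6% |
| 20% | 5 | 1.0 | 18.2% |
| 30% | 5 | 1.5 | 34.8% |

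**4. Check with a different model.** Suppose the least engaged fraction of treated families is dropped and engagement has correlation *r* with the change score (SD 9.07). Dropping 20% with r from 0.1 to 0.3 gives 0.32 to 0.95 points and type I error of 6.3% to 17.1%. Dropping 30% gives 0.45 to 1.35 points and 7.6% to 29.8%. With r = 0 there is no bias. The two models agree in order of size.

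**5. A real effect in players only.** Take 3.1 points in players, none in non-players, and d = 0. The ITT effect among families who would answer is (1 − s) × 3.1 = 2.79, 2.48 and 2.17 for s = 10%, 20% and 30%. The t-test would estimate 3.1, which is too high by 1/(1 − s) − 1 = 11%, 25% and 43%.

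**6. Families passed over.** Reaching 180 treated completers would leave out 180 × s/(1 − s) = 20, 45 or 77 treated families who would have answered.

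**The case against.** The strongest reply is that the plan never says the mark ends outcome collection. Section 8.1 asks both arms for week-4 measures without qualification, and silence about families marked lost does not create an exception. An email request in 8.1 (printed under Week 8 but timed at week 4) is counted from app download, not from play. The gift card in section 6.4 is paid for completing measures, so some non-players have a reason to answer. This stands: the selection is possible, not stated.

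The rule also speaks of participants, not treated families, and does not define activity. Section 8.1 has everyone download the app before allocation, so a control's log-in might count, and a family that never downloads is never randomized. Section 7.2, by contrast, sends the download link to treatment participants. The one-arm reading rests on the Treatment Compliance heading, on the neighbouring sentence about using the app, and on controls having nothing to play. Even if log-ins count, the criterion differs by arm: playing a game against opening a waiting message.

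The sentence could also mean that a family unreachable after three contacts is recorded as lost, which is ordinary practice. A family that replies but does not play would then not be lost. The text allows this reading as well.

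Finally, nothing in the documents supports particular values of s or d, and the 35% figure puts both at their upper limits.

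**Conclusion.** The concern holds as a defect in a stated rule whose consequence is conditional. Section 7.2 can be read as marking families lost for app inactivity. If that mark stops the week-4 request, the primary comparison is treated players against all responding controls.

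A reader might infer that the plan does remove inactive treated families from the analysis, or that type I error is about 35%. The documents support neither. Week-4 measures are requested of both arms, ITT is named, and the range of 0 to 1.5 points and 5% to 35% depends wholly on the assumed s and d and on an SD implied by the power statement. The middle case (s = 20%, d = 3) is 0.6 points against a 3.1-point target, with type I error of 9.6%. With d = 0 there is no bias under the null.

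It should be fixed, with medium confidence. The wording is easily changed, whereas week-4 scores that were never requested cannot be recovered later.

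**What to change.** In section 7.2:

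- State that app inactivity triggers reminders to play but never changes follow-up status.
- Send every randomized family in both arms, including those who never play, the same week-4 request and the same number of survey reminders on the same schedule.
- Define lost to follow-up, in both arms, only as week-4 measures not returned after those reminders.

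In the descriptive analyses of section 10.5, report week-4 return by arm and, in the treatment arm, by any versus no play.

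The cost is a few sentences and some additional emails. Inactive families who answer count toward the 360, so the completer target does not rise. The estimated effect may be smaller, because non-players stay in the treatment arm. If recruitment has begun, report how many treated families were marked lost for inactivity and send the request to those still in the week-4 window.

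This equalizes the request for outcomes. It does not deal with families who are asked and do not answer; they still drop out of the t-test.
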